### 5.4.3. Tapering of Itacitinib/Placebo

If a subject has achieved CR or VGPR at Day 180, investigators may begin to taper the dose of itacitinib/placebo by 1 dose level provided corticosteroids have been discontinued for at least 8 weeks following institutional guidelines. Subsequent tapering may occur within 28 to 56 days after the initial taper as appropriate.

Subjects who are still receiving calcineurin inhibitors or other agents for GVHD prophylaxis at this time may continue to do so at the treating investigator's discretion. In addition, subjects must not be experiencing any Grade 2 or higher hematologic toxicity related to study treatment or symptoms of an active infection.

Investigators wishing to initiate a taper of itacitinib/placebo at an earlier timepoint may do so upon consultation with and approval from the sponsor's medical monitor.

If GVHD signs/symptoms worsen during the taper of itacitinib/placebo, the dose may be escalated by 1 dose level. If the subject requires additional systemic therapy (includes restarting of corticosteroids), then the subject would be considered as having progression of disease and

would be withdrawn from study treatment. A physiologic dose of 6 to 8 mg/day of methylprednisolone (ie, 7.5-10 mg/day of prednisone) during itacitinib/placebo taper is allowed and will not be considered treatment failure.

If subjects completely taper off itacitinib/placebo and GVHD signs/symptoms reappear at a later time, subjects may enter the re-treatment phase at the investigator's discretion (Section 6.4). Assessments would be performed as per the re-treatment assessment schedule listed in Table 3.

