#### 9.4.2. Secondary Analyses

The key secondary endpoint is NRM at Month 6, defined as the proportion of subjects who died due to causes other than malignancy relapse at Month 6. The comparison of NRM at Month 6 between treatment cohorts will be conducted using a 2-sample proportion test with normal approximation. Summary statistics and 95% CI will be provided.

Additional secondary endpoints will be analyzed as follows:

- ORR, defined as the proportion of subjects demonstrating a CR, VGPR, or PR at Days 14, 56, and 100. The comparison between treatment cohorts will be conducted using a 2-sample proportion test with normal approximation. Summary statistics and applicable 95% CI will be provided.
- NRM, defined as the proportion of subjects who died due to causes other than malignancy relapse at Months 9, 12, and 24. The comparison between treatment cohorts will be conducted using a 2-sample proportion test with normal approximation. Cumulative incidence rates will be provided. Summary statistics and applicable 95% CI will be provided.
- DOR, defined as the time from first response until GVHD progression or death. The comparison between treatment cohorts will be conducted using the log-rank test. The Kaplan-Meier method will be used. Summary statistics will be provided.
- TTR, defined as the interval from treatment initiation to first response.
- Relapse rate of malignant and nonmalignant hematologic diseases, defined as the proportion of subjects whose underlying disease relapses. The comparison between treatment cohorts will be conducted using a 2-sample proportion test with normal approximation. The cumulative incidence rate and summary statistics will be provided.

- Relapse-related mortality rate, defined as the proportion of subjects whose malignancy relapses and has a fatal outcome. The comparison between treatment cohorts will be conducted using a 2-sample proportion test with normal approximation. The cumulative incidence rate and summary statistics will be provided.
- FFS, defined as the proportion of subjects who are still alive, have not relapsed, have not required additional therapy for aGVHD, and have not demonstrated signs or symptoms of cGVHD, at Month 6. The comparison between treatment cohorts will be conducted using the log-rank test. The Kaplan-Meier method will be used. Summary statistics will be provided.

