2.2. Study Objectives and Endpoints

[Table 1](#) presents the study objectives and endpoints.

Table 1: Objectives and Endpoints

Primary Objective	Primary Endpoint
Compare the efficacy of itacitinib in combination with corticosteroids versus placebo in combination with corticosteroids in terms of ORR at Day 28 in subjects with aGVHD.	ORR at Day 28, defined as the proportion of subjects demonstrating a CR, VGPR, or PR.
Key Secondary Objective	Key Secondary Endpoint
Compare the efficacy between treatment cohorts at a subsequent key clinical landmark.	NRM at Month 6, defined as the proportion of subjects who died due to causes other than malignancy relapse at Month 6.
Secondary Objectives	Secondary Endpoints
Compare additional response and longer-term efficacy outcomes between treatment cohorts.	ORR, defined as the proportion of subjects demonstrating a CR, VGPR, or PR at Days 14, 56, and 100.
	NRM at Months 9, 12, and 24.
	DOR for responders will be calculated. The DOR is defined from the time of the onset of response to loss of response. Subjects who died or discontinued will be censored at the death date or the previous assessment.
	TTR, defined as the interval from treatment initiation to first response.
	Relapse rate of malignant and nonmalignant hematologic diseases, defined as the proportion of subjects whose underlying hematologic disease relapses.
	Malignancy relapse-related mortality rate, defined as the proportion of subjects whose malignancy relapses and has a fatal outcome.
	FFS, defined as the proportion of subjects who are still alive, have not relapsed, have not required additional therapy for aGVHD, and have not demonstrated signs or symptoms of cGVHD, at Month 6.
OS, defined as the interval from study enrollment to death due to any cause.	
Assess the incidence and severity of AEs and SAEs.	Clinical safety data (eg, AEs, infections) will be tabulated and listed.
Evaluate the PK of itacitinib when administered in combination with corticosteroids.	C_{max} , C_{min} , t_{max} , AUC, and CL/F.
Evaluate the incidence of secondary graft failure.	Incidence rate of secondary graft failure, defined as > 95% recipient cells any time after engraftment with no signs of relapse, OR retransplantation because of secondary neutropenia ($< 0.5 \times 10^9/L$) and/or thrombocytopenia ($< 20 \times 10^9/L$) within 2 months of transplant.

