7.1. General Considerations

In all efficacy analyses, initiation of new, systemic anti-GVHD therapy includes 2 scenarios:

1) initiation of new anti-GVHD therapy including a higher dose of corticosteroid than that used at Day 1 and 2) initiation of new, systemic anti-GVHD therapy when subjects who were treated with placebo in the treatment phase were re-treated with itacitinib in the retreatment phase.

Initiation of new, systemic anti-GVHD therapy will be considered when defining the following:

1) onset of response and 2) loss of response. When defining responder for Day 28 ORR; overall response at Days 14, 56, 100, and 180; and BOR, the onset of response will be censored by initiation of new, systemic anti-GVHD therapy. Responders who did not have GVHD progression or death after response will be censored at the time of either study withdrawal, initiation of new, systemic anti-GVHD therapy, or the date of last assessment of GVHD before or on the cutoff date, whichever is earliest. In the survival analysis of NRM, all subjects in the analysis set in question without a death due to causes other than malignancy relapse will be censored at either study withdrawal, death due to malignancy relapse, or the date of last contact before or on the cutoff date, whichever is earliest.

Duration of response will be calculated for every subject who has a response in the study; DOR will also be summarized for any subgroups of interest.

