7.3.2. Duration of Response for Day 28 Responders

The DOR is defined from the time of the first response to the loss of response (ie, either disease progression or death). Responders who did not progress or die after onset of response will be censored, and response will be ended at either study withdrawal, initiation of new anti-GVHD therapy, or last response assessment before or on the cut-off date, whichever is earliest.

Duration of response will be calculated for every responder as well as Day 28 responders.

The DOR for the Day 28 responders will be assessed using the KM method only for subjects who achieve Day 28 response. The KM curves; medians; 1-, 2-, 6-, 12-, 18- and 24-month (equivalently at Days 30, 60, 180, 365, 547, and 730) survival estimates and 95% CIs will be estimated ([Brookmeyer and Crowley 1982](#)). The DOR will be assessed for each treatment group and also by stratum and Day 28 response status.

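### Duration of response has opposite rules for death in the endpoint tables and the analysis sections, and its main analysis censors new anti-GVHD therapy that the documents elsewhere treat as failure

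*SAP*

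**What the plan says.** **Death.** The Protocol Synopsis, Protocol Section 2 and SAP Table 1 (SAP 2.2) carry the same sentence: "Subjects who died or discontinued will be censored at the death date or the previous assessment". Protocol 9.4.2 has: "DOR, defined as the time from first response until GVHD progression or death". SAP 7.3.2 has: "The DOR is defined from the time of the first response to the loss of response (ie, either disease progression or death". SAP 7.1 agrees with 7.3.2, because it censors only responders who had neither progression nor death.

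**New anti-GVHD therapy.** Under SAP 7.3.2, responders who neither progressed nor died "will be censored, and response will be ended at either study withdrawal, initiation of new anti-GVHD therapy, or last response assessment". SAP 7.1 gives the same rule: "censored at the time of either study withdrawal, initiation of new, systemic anti-GVHD therapy". SAP 7.1 defines new therapy to include a corticosteroid dose above the Day 1 dose. It also lists new therapy among the things considered in defining loss of response, then censors at it.

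**Alternates.** SAP 7.3.3 specifies two further DOR definitions. Both count death and new therapy as events, and both start at Day 28 rather than at first response.

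**Changes.** SAP 10.1, on changes to protocol-defined analyses, does not mention DOR.

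**The concern.** DOR is a named secondary efficacy endpoint, and Protocol 9.4.2 compares it between arms with a log-rank test. The table rule and the analysis-section rule are different endpoints. One estimates time to progression with deaths removed; the other estimates time alive and without progression. A reader of the tables would expect one and be given the other.

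The new-therapy rule is a second, separate matter. Other sections treat the same event as a failure:

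- Protocol 4.1: a need for additional systemic therapy is treatment failure.
- Protocol 5.2.3: so is a need for corticosteroids above the starting dose.
- Protocol Appendix B: patients receiving secondary therapy are nonresponders.
- SAP 7.4.9: new anti-GVHD therapy is a failure-free survival event.

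Protocol 6.5.2 ends post-treatment GVHD follow-up when new therapy starts, so a later progression may never be recorded. A responder who needs more treatment can therefore leave the DOR analysis as censored, with no event counted.

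**Working it through.** The documents give no sample size, power or event count for DOR, so there is no figure of theirs to reproduce. The check has three parts.

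**1. Direction within an arm.** Each Kaplan-Meier event time contributes a factor (1 − d/n), with d events among n at risk. If an event is recoded as censored at the same date, later risk sets do not change and its factor gets larger or becomes 1. The curve can then only stay equal or rise. In 500 simulated data sets with three recodings each (death, new therapy, both), the curve never fell.

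**2. Size, under assumed rates.** Take independent constant hazards, progression median m days, and, by time T, death risk d and risk of new therapy without recorded progression n. The proportion still in response at T is

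S = 2^(−T/m) × (1 − d) × (1 − n),

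and a factor drops out when that event is censored.

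Inputs:

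- m = 130 and 189.5 days, the lowest and highest Phase 1 median DOR in Protocol 1.4.2. Reading them as progression medians is an assumption; that study mixed first-line and steroid-refractory subjects.
- d = 5 to 33% by Day 180. This is assumed; the upper values 19.8% and 33% are the planned Day 180 NRM rates for all subjects (SAP 3.3).
- n = 5 to 20% by Day 180, assumed.

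The progression factor at Day 180 is 2^(−180/130) = 0.383 or 2^(−180/189.5) = 0.518. With m = 130, d = 10% and n = 10%:

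| Rule | In response at Day 180 | Median (days) |
|---|---|---|
| Death and new therapy both events | 0.383 × 0.90 × 0.90 = 31.0% | 107 |
| Either one censored | 0.383 × 0.90 = 34.5% | 117 |
| Both censored | 38.3% | 130 |

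Across the ranges, relative to counting both as events:

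- Death censored: from 0.383 × 0.80 × 0.05 = 1.5 points to 0.518 × 0.95 × 0.33 = 16.2 points, so about 2 to 16.
- New therapy censored: from 0.383 × 0.67 × 0.05 = 1.3 points to 0.518 × 0.95 × 0.20 = 9.8 points, so about 1 to 10.
- Both censored: about 4 to 24 points.

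At 12 months, leaving new therapy aside, the gap from censoring death is 2^(−365/m) × d. The progression factors are 0.143 and 0.263, so 12-month progression is about 86% and 74%. With 12-month death risk of 15 to 30%, the gap runs from 0.143 × 0.15 = 2.1 points to 0.263 × 0.30 = 7.9 points. If 12-month progression were only 30%, it would run from 0.70 × 0.15 = 10.5 points to 0.70 × 0.30 = 21 points.

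**3. Between arms.** Let both arms have the same progression hazard (median 160 days, assumed).

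- Day 180 death of 15% on placebo and 8% on itacitinib, with new therapy at 10% in each arm: hazard ratio 0.92 with deaths counted, 1.00 with deaths censored.
- New therapy of 20% and 10%, with death at 10% in each arm: 0.89 with it counted, 1.00 with it censored.

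Swapping the arms puts the hazard ratio above 1 when the event is counted. The coding rule can move the comparison, but the documents do not fix the direction.

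**The case against.** The strongest reply on death is that every operative section (Protocol 9.4.2, SAP 7.1, 7.3.2 and 7.3.3) already counts it as an event. The tables would then be a wording error, and a reader should not infer that the planned analysis will in fact censor deaths. That stands. What remains is a contradiction inside both documents on a named endpoint, which SAP 10.1 does not resolve.

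On new therapy, three limits stand.

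- Only responders with no earlier recorded progression are affected, and their number is unknown.
- The two alternates in SAP 7.3.3, and failure-free survival, already count new therapy as an event. The alternates start at Day 28, however, and so do not replace the main definition from first response.
- Protocol 5.4.3 says of a subject needing additional systemic therapy: "then the subject would be considered as having progression of disease". A reader might infer that the protocol calls all new therapy progression. That sentence concerns worsening during the study-drug taper only, and where it applies the subject already has a DOR event under SAP 7.3.2. The general point rests on Protocol 4.1, 5.2.3 and Appendix B and on SAP 7.4.9.

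A reader might also take the calculation as proof of informative censoring. It is not: with independent hazards, the gap is a change in what is estimated. Informative censoring at new therapy is plausible, because such therapy is given when GVHD control is inadequate, but nothing here measures it.

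**Conclusion.** The concern holds as a contradiction on death and, secondarily, as a questionable main rule for new therapy. Relative to a composite of progression, death and new therapy, censoring either event (at its own date) cannot lower an arm's curve. Censoring death adds about 2 to 16 points at Day 180 under the assumed ranges. At 12 months it adds about 2 to 8 points with the Phase 1 medians read as progression medians.

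Three stronger readings are not supported:

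- **An overstatement of 10.5 to 21 points.** This requires 12-month progression as low as 30%, which no figure in the documents suggests.
- **Bias in favour of itacitinib.** The between-arm direction depends on which arm has more deaths or more new therapy.
- **A threat to the main conclusions.** DOR lies outside the multiplicity-controlled endpoints (SAP 3.2), so the Day 28 ORR and Month 6 NRM tests do not change.

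All event rates here are assumptions, not trial data.

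**What to change.** First, correct the DOR entry in the Protocol Synopsis, Protocol Section 2 and SAP Table 1 so that death is loss of response, matching Protocol 9.4.2 and SAP 7.1 and 7.3.2. This is a wording change.

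As a secondary change, count new systemic anti-GVHD therapy, as SAP 7.1 defines it, as loss of response in the main DOR analysis. Make the same edit in SAP 7.1, SAP 7.3.2 and Protocol 9.4.2; changing 7.3.2 alone would create a new conflict. Keep censoring at new therapy as a labelled sensitivity analysis. Report, by arm, how many responders have death or new therapy as their first event, so that the effect of the rule can be seen.

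The cost is a small reprogramming of the main DOR derivation and somewhat shorter reported durations. SAP 7.3.3 already requires death and new therapy to be derived as events, so no new data are needed. Only the analysis rule changes, not patient management.

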3. STUDY DESIGN

This is a randomized, double-blind, placebo-controlled, multicenter Phase 3 study of itacitinib or placebo in combination with corticosteroids as first-line treatment of subjects with Grade II to IV aGVHD. Subjects will be randomized 1:1 to itacitinib 200 mg plus corticosteroids or matching placebo plus corticosteroids. Randomization will be stratified by GVHD risk status (ie, standard risk vs high risk; [MacMillan et al 2015](#)). Subjects will receive randomized study treatment until treatment failure (progression of disease, no response, or requiring additional systemic therapy), unacceptable toxicity, or death. Transfusion support and continued use of anti-infective medications, GVHD prophylaxis medications (including calcineurin inhibitors), and topical steroid therapy are permitted.

[figure not shown]
GVHD staging and grading will be assessed for efficacy as per MAGIC criteria ([Harris et al 2016](#)); safety and tolerability will be assessed as per NCI CTCAE v4.03 ([NCI 2010](#)).

An independent DMC will perform an interim analysis for futility once 112 subjects (around 56 per cohort) have completed the Day 28 visit or withdrew early from the study. If the futility boundary is crossed at Interim Analysis 1, the sponsor may consider stopping the study. A second interim analysis for the primary endpoint of Day 28 ORR (both efficacy and futility) will be performed once 240 eligible subjects have completed the Day 180 visit or withdrew early from the study. If the Day 28 ORR efficacy boundary is crossed, the Day 180 NRM will be tested.

The final analysis will be conducted once the last subject completes the Day 180 visit or withdraws from the study.

[figure not shown]
[Figure 1](#) below depicts study design at screening and randomization, and [Figure 2](#) summarizes study flow after randomization.

Figure 1: Study Design: Screening and Randomization

R = randomization.

Figure 2: Study Design: Study Flowchart

Note: Methylprednisolone is given at 2 mg/kg per day or at a dose per local treatment guidelines. Some subjects started with 1 mg/kg per day on Day 1, and this is accepted per the Protocol.

3.1. Randomization

Randomization will occur centrally by the IVRS. Subjects will be randomized in a 1:1 ratio to receive itacitinib plus corticosteroids or matching placebo plus corticosteroids and will be stratified by baseline GVHD risk status (ie, standard-risk versus high-risk). As this is a randomized, double-blind, placebo-controlled study, neither the investigators nor the sponsor will be aware of the treatment to which a subject is randomized.

3.2. Control of Type I Error

For the primary and key secondary endpoints, the overall 1-sided Type 1 error is controlled at 0.025. Early stopping for positive efficacy is permitted in this study. Testing of the primary endpoint will use an alpha-spending approach to control Type I error. Subsequent testing of the key secondary endpoint will control Type I error using the Bonferroni method. See Sections 3.4 and 9 for more details.

No multiplicity adjustment will be applied to other endpoints. For estimation purposes, 95% CIs will be provided for parameter estimates of other endpoints.

3.3. Sample Size Considerations

A sample size of 414 subjects with 1:1 randomization (itacitinib vs placebo) and stratification based on baseline aGVHD risk status (standard risk vs high risk) provides approximately 90% power to test for the primary endpoint (ORR at Day 28) and approximately 80% power to test for the key secondary endpoint (NRM rate at Month 6). The family-wise α -level will be controlled at 0.025 overall for the two comparisons. Specifically, this study will claim to have achieved the efficacy objective when the primary endpoint ORR at Day 28 shows a significant treatment effect at 1-sided $\alpha = 0.025$. Conditional on significance of the primary endpoint, the key secondary endpoint (NRM rate at Month 6) will be tested at 1-sided $\alpha = 0.025$.

An absolute improvement of 16% in the primary endpoint of ORR at Day 28 would be considered a clinically meaningful improvement over standard first-line systemic treatment for aGVHD. A sample size of 414 subjects (207 subjects per treatment group) will provide approximately 90% power to detect a 16% overall difference (72% vs 56%) between treatment groups for the primary endpoint (ORR at Day 28) at a 1-sided alpha level of 0.025.

The assumed Day 28 ORR of 56% is based on MacMillan et al (2015). The stratum-specific response rates (standard risk, 68%; high risk, 44%) assume a standard risk:high risk ratio of 0.50:0.50. It is expected that treatment with itacitinib will result in a 16% increase in the ORR, that is, an expected odds ratio of 2.02 (which corresponds to an overall increase in ORR to 72%), with stratum-specific response rates of 81% and 61% for standard-risk and high-risk aGVHD cohorts, respectively. Power for the CMH test with stratification based on GVHD risk score was calculated using software N-Query 5.0.

[figure not shown]
Given its clinical significance, NRM rate at Month 6 will be assessed as the key secondary endpoint. The Day 180 NRM rate difference between 2 groups is tested using a KM estimator of the cumulative distribution function at Day 180. Based on MacMillan et al (2015), the overall NRM at Month 6 in the best available therapy group is 33%, with a stratum-specific NRM rate of 22% for standard risk and 44% for high risk (assuming a standard risk:high risk ratio of 0.50:0.50). A 40% relative reduction in NRM rate will be considered a clinically meaningful improvement. Based on simulation, a sample size of 414 subjects (207 subjects per treatment cohort) will provide approximately 80% power to detect a relative reduction of 40% (or absolute difference of 13.2%, ie, 19.8% vs 33% at Day 180) between treatments at a 1-sided α level of 0.025. NRM at Month 6 will be tested using a CMH test stratified by risk status (standard-risk vs high-risk aGVHD). Stratum-specific NRM rates of 12.4% and 28.2% are expected for standard-risk and high-risk cohorts, respectively. Power for the CMH test with stratification based on GVHD risk score was calculated using software N-Query 5.0.

In order to compensate for an anticipated early withdrawal rate of up to 5% (ie, subjects who do not have any response data before Day 28), a total of 436 subjects (218 per treatment arm) will be randomized into the study to ensure a sample size of 414 evaluable subjects.

